During the course of the SCIN trial we developed a standardised validated method of screening for hand dermatitis using photographic images.(13) Several other studies have indicated that diagnostic decisions based on photographic images of localized skin regions are comparable with face-to-face assessments by dermatologists, since it allows clinicians to zoom in on distinct skin areas where early signs of disease are present.(14,15) Previous

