#### **NHS Foundation Trust**

teledermatology studies have also shown them to be flexible and feasible to deliver in large, geographically dispersed occupational groups with noteworthy cost-benefits.(16,17) It is important that we now test our screening tools in clinical staff other than intensive care nurses, and in non-clinical staff for example laboratory workers. We also need to ensure that our screening tools are equally effective when applied to all Fitzpatrick skin phototypes as there are challenges in recognising the typical clinical features of dermatitis in skin of colour, especially given that a high proportion of NHS workers have darker skin type. For the purpose of this study, we will use a slightly modified Fitzpatrick Skin-Type Chart tool.

We postulate that screening by a single-item questionnaire with follow-up of those reporting possible hand dermatitis by teledermatology using selfie hand photographs taken with a mobile phone camera, would be a novel, and time- and cost-effective, approach to optimise and improve health surveillance for hand dermatitis in healthcare staff. If our suggested method is found to be feasible, acceptable, and effective, it has the potential to revolutionise the early detection and management of hand dermatitis in the healthcare sector.

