Hand photographs (form 3 only) will be accessible to the study nurse via the REDcap portal and the study nurse will assess the presence of dermatitis using the Validated Investigator Global Assessment for Atopic Dermatitis (vIGA-AD) tool (20). Within the portal, the study nurse will then assign and score the photographs to five categories as per IGA score (Category 1: 'Clear'; Category 2: 'Almost clear'; Category 3: 'Mild'; Category 4: 'Moderate'; Category 5: 'Severe') with the first indicating 'absence of dermatitis' and any of the categories 2-5 indicating 'presence of dermatitis'. The dermatology nurse will also keep a separate category for the photographs for which they are unsure and another category for photographs which are insufficiently clear for assessment and which participants will be invited by the research team to resubmit new hand photographs. For the unsure cases, the photographs will be assessed by the dermatologist via the REDcap portal (form 3 only). Information on whether participants' hand photographs require further assessment by the study dermatologist (i.e. categorised as 'Unsure' by the study nurse) will also be recorded in REDcap, as it is relevant for future application of surveillance method.

Participants who provide photographs that are not sufficiently clear for assessment will be recontacted by a member of the central study team (not the study dermatologists or dermatology nurse) and invited on one occasion only to provide an additional set of hand photographs. In order to ensure that the photograph is taken within 3 days of the time as they are being assessed for presence of hand dermatitis, we will require them to re-answer the question *'In your opinion do you have hand/wrist dermatitis/eczema)?'* with answer options of *yes/no or unsure*. Those who answer 'yes', or 'unsure' will then be asked the question:

'*where is your hand/wrist dermatitis or skin condition located?*'. A separate form (form 6) will be used to collect re-submitted hand photographs. Photographs that the dermatology nurse deems to be of too poor quality to assess will not be included in the final analysis.

Prior to assessing the presence of dermatitis, to ensure appropriate use of the vIGA-AD tool, the dermatologist nurse will be required to complete a training consisting of a video on best practices for using the scale to rate the severity of the disease and subsequently complete a certification examination as described by Simpson et al. (20)

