Once the study nurse is fully trained, they will independently assess all hand photographs. After nurse's assessment has been completed, the presence or absence of dermatitis (vIGA score Categories 2-5 and Category 1, respectively) will be compared with participants' self-responses.

Photographs on discordant pairs (outcomes 2 and 3 described below) will be further assessed by the two study dermatologists who will assess presence of dermatitis. The dermatologist will independently assess the hand photographs for presence of hand dermatitis and score 1-5 on the vIGA scale. If the dermatologists' scores differ they will agree a score by discussion. The original nurse's assessment using the vIGA tool will be corrected for the dermatologists' expert opinion where needed.

The nurse's assessment of the hand photographs and any back up required by the study dermatologist with correction of the assessment on the vIGA scale where needed, will be considered the gold standard against which the questionnaire-based self-assessed presence of dermatitis (new proposed screening tool) will be compared. We will assess the acceptability of the self-assessment screening tool by incorporating several short questions into the study questionnaires.

The questionnaire we will also include several questions to capture participants views on the study material, and the instructions they have to follow to complete the self-assessment screening questionnaire and for taking and submitting hand photographs. Response options will be set out in Likert scale format to aid analyses of results. We will further ask their willingness to involve their line-managers in the skin surveillance. The questionnaire will also include the option for participants to provide further qualitative (free text) feedback on a) concerns about completing the questionnaires and/or uploading photos, b) on obstacles and facilitators to implementation of the proposed methods, and c) anything not covered by the questions above.

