## **12 STATISTICAL CONSIDERATIONS**

The following outlines the proposed statistical analyses methods planned as they relate to each research question (RQ).

• RQ1 Can a self-assessed hand dermatitis screening questionnaire for at-risk health care workers reliably be used as part of a health surveillance programme?

As the primary study outcome, we will calculate the sensitivity of the proposed selfassessment screening tool (single-item self-reported dermatitis) along with its 95% confidence intervals when compared with the gold standard (nurse's dermatitis assessment from the hand photographs). We will further assess its specificity, positive and negative predictive value. The analysis will be conducted for all participants and then separately by medium and high risk of hand dermatitis, determined by frequency of hand washing 10-20 times per day (medium risk), and more than 20 times per day (high risk).

• RQ2 What is the sensitivity and specificity of the hand dermatitis self-assessment screening questionnaire in identifying early hand dermatitis, and is it similar across all Fitzpatrick skin phototypes and occupational (clinical vs non-clinical) groups?

The accuracy of hand dermatitis self-assessment screening questionnaire will further be explored in sub- groups of our sample participants. Primarily sensitivity, and specificity, and further positive and negative predictive values, as indicators of the accuracy of the screening test will be estimated for clinical and non-clinical staff and their differences will be compared statistically. Due to the high number of NHS staff of non-white ethnic origin, and the lack of information about hand dermatitis or ability to self-report its presence across the six Fitzpatrick skin phototypes, we will also stratify our results by Fitzpatrick phototypes, with a potential to identify skin phototypes in which accuracy of the screening questionnaire is lower.

• RQ3 Is the self-assessment screening questionnaire and photographic method acceptable and feasible to use in healthcare staff in a busy NHS setting?

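### RQ2 reads phototype differences as differences in questionnaire accuracy, but the photographic reference is unchecked by phototype, so the comparison can be distorted in either direction and may well hide a real deficit

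*Protocol*

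**What the plan says.** Similarity of accuracy across phototypes is part of a stated research question (Section 4.1, RQ2) and is listed under the primary objective in the synopsis. Section 12 stratifies the results by phototype "with a potential to identify skin phototypes in which accuracy of the screening questionnaire is lower".

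Section 7.3 says that the nurse's photograph assessment, corrected by dermatologists where needed, "will be considered the gold standard against which the questionnaire-based self-assessed presence of dermatitis (new proposed screening tool) will be compared". Photographs go beyond the nurse by two routes:

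- "The dermatology nurse will also keep a separate category for the photographs for which they are unsure", and a dermatologist reads those.
- "Photographs on discordant pairs (outcomes 2 and 3 described below) will be further assessed by the two study dermatologists".

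Section 7.4 labels a negative questionnaire with a negative nurse reading a true negative, with no further reading.

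On the reference itself, the Introduction refers to a "standardised validated method of screening for hand dermatitis using photographic images" and says that "diagnostic decisions based on photographic images of localized skin regions are comparable with face-to-face assessments by dermatologists". Neither statement is broken down by phototype. The Introduction also says "We also need to ensure that our screening tools are equally effective when applied to all Fitzpatrick skin phototypes", giving as the reason that "there are challenges in recognising the typical clinical features of dermatitis in skin of colour".

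**The concern.** Sensitivity against an imperfect reference mixes the errors of the test with those of the reference. If the photograph reading is less accurate in some phototypes, the phototype comparison no longer isolates the questionnaire. The protocol gives a reason to expect this: its remark about recognising dermatitis in skin of colour is not limited to self-assessment, and the photographic method is one of the tools whose performance by phototype is still open.

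The safeguards do not settle it. Reader training, review of unsure cases and re-reading of discordant pairs are not specific to phototype, and none looks beyond photographs. A case missed by both participant and nurse is never re-read unless the nurse was unsure, and it leaves the sensitivity denominator. Such shared misses are most likely where dermatitis is hardest to see.

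At stake is whether RQ2 can support a statement that the questionnaire works less well, or equally well, in darker skin. Section 17 links the findings to recommendations for wider NHS use.

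**Working it through.** **The plan's own figure.** Section 12.1 gives 231 per group from sensitivity 0.90, distance 0.10 to the lower bound and prevalence 0.15: 1.96² × 0.90 × 0.10 / (0.10² × 0.15) = 230.5, so 231, and 6 × 231 = 1386. This reproduces. The formula takes the reference as error-free.

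**Inputs.** Prevalence p = 0.15, equal across skin types, is from Section 12.1. Questionnaire specificity Sp = 0.90 and all reader accuracies are assumptions; the protocol gives none. Dermatologists are first given the nurse's sensitivity Rs and specificity Rp. Errors are independent given true status, except for a covariance c between participant and nurse among true cases. The unsure and unassessable routes are left out.

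**Model of the planned re-reading** (discordant pairs only; Se is true questionnaire sensitivity):

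- TP = p[Se·Rs(2 − Rs) + c(1 − Rs)] + (1 − p)(1 − Sp)(1 − Rp)(1 + Rp)
- FN = p·Rs[(1 − Se)Rs − c] + (1 − p)·Sp·(1 − Rp)²
- Apparent sensitivity = TP / (TP + FN)

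**A real deficit, Se = 0.70, readers 0.70/0.95.**

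- c = 0: TP = 0.15 × 0.70 × 0.70 × 1.30 + 0.85 × 0.10 × 0.05 × 1.95 = 0.09555 + 0.00829 = 0.10384. FN = 0.15 × 0.70 × 0.21 + 0.85 × 0.90 × 0.0025 = 0.02205 + 0.00191 = 0.02396. Apparent sensitivity 0.81.
- c = 0.10 (the maximum here is 0.21): TP = 0.10384 + 0.15 × 0.10 × 0.30 = 0.10834. FN = 0.15 × 0.70 × 0.11 + 0.00191 = 0.01346. Apparent sensitivity 0.89.

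The distortion is 11 to 19 points, against a design precision of 10 points.

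**Better dermatologists do not remove it.** With error-free dermatologists and the same nurse, TP = p·Se + (1 − p)(1 − Sp)(1 − Rp) = 0.105 + 0.00425 = 0.10925 and FN = p[(1 − Se)Rs − c]. For c = 0, FN = 0.15 × 0.21 = 0.0315 and apparent sensitivity is 0.78. For c = 0.10, FN = 0.15 × 0.11 = 0.0165 and it is 0.87. The shared misses are never seen.

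**No real difference, Se = 0.90 in every phototype, c = 0.**

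| Readers (sens/spec) | Apparent sensitivity, nurse only | Apparent sensitivity, discordant pairs re-read |
|---|---|---|
| 0.95/0.99 | 0.855 | 0.909 |
| 0.80/0.95 | 0.691 | 0.923 |
| 0.70/0.85 | 0.461 | 0.856 |

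The nurse-only formula is [p·Rs·Se + (1 − p)(1 − Rp)(1 − Sp)] / [p·Rs + (1 − p)(1 − Rp)]. With re-reading, an unchanged questionnaire can look slightly better or, if reader specificity is also poor, worse.

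**The case against.** A reader might infer that reference error will make the questionnaire look much worse in darker skin. The nurse-only column seems to show it: 0.855 against 0.691, a false gap of 16 points, and Section 12 does describe the reference in brackets as the nurse's assessment. The documents do not support that reading. Sections 7.3 and 7.4 send every discordant pair to two dermatologists before it is classed as a false positive or false negative, and with that step the same inputs give 0.91 against 0.92. Most of the 16 points also comes from the assumed fall in reader specificity: lowering only reader sensitivity from 0.95 to 0.80 at specificity 0.99 moves the nurse-only figure from 0.855 to 0.847. Difficulty in recognising dermatitis points to missed cases rather than to false positives.

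Other points are fair. The protocol never says that photograph reading is less accurate in dark skin; that is an inference from its general remark. RQ2 is worded as exploratory. Tables of unsure and overturn rates, and a sensitivity analysis for the reference, could sit in a statistical analysis plan that is not shown, so it cannot be said that these data will go unused. A bias analysis without independent verification rests on assumed ranges.

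What remains is that the protocol itself fixes the reference, the discordant-only re-reading and the reading of a phototype gap as questionnaire accuracy.

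**Conclusion.** The point holds as a limit on what RQ2 can conclude. Neither a lower nor an equal sensitivity in a phototype can be assigned to the questionnaire from the planned comparison alone. Under the planned re-reading the likelier error is a masked deficit: a true 0.70 appears as about 0.81, or 0.89 with shared misses, above the 0.80 minimum that three of the four responding physicians gave.

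That comparison is of point estimates. If a skin group has 462 people (two groups of 231), about 59 and 56 would be reference-positive (462 × 0.1278 and 462 × 0.1218). The simple (Wald) 95% lower limits are then 0.71 and 0.81, and the second becomes 0.78 with the Wilson method. Only strong shared misses would bring a phototype truly at 0.70 close to the lower-bound target.

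The size rests on assumed reader accuracy, on independence between nurse and dermatologist errors, and on ignoring the unsure route. If dermatologists, seeing the same photographs, simply repeated the nurse's errors, the results would move towards the nurse-only figures (0.53 in place of 0.81). That is why the direction cannot be taken as certain. The sample size is not affected.

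**What to change.** In Section 12 (RQ2), with a matching line in Section 7.3:

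- Keep the nurse's score before correction as a separate field.
- Report by phototype both nurse-only and adjudicated sensitivity and specificity, with the nurse-unsure, unassessable-photograph and dermatologist-overturn rates.
- Add a bias analysis over stated ranges of reader sensitivity and specificity by phototype. It should model re-reading of discordant pairs only and allow correlated misses between participant and nurse.
- Word the conclusion as 'agreement with photographic assessment' by phototype. Claim lower or equal questionnaire accuracy only if that holds across the stated ranges.

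The cost is one table, one analysis and a more cautious conclusion, using data that the study already collects; no in-person examination is needed. Two limits remain. The ranges are assumptions, and overturn rates come from re-read photographs, so they say nothing about concordant negatives.

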#### 12.1 Statistical power

Considering as the primary study outcome the sensitivity of the single-item questionnaire (with secondary outcomes being its specificity, positive and negative predictive value) we enquired six occupational physicians with experience in NHS work what they would consider as the minimum acceptable sensitivity for such a self-assessment screening tool (single-item questionnaire) to be administered by managers to detect hand dermatitis in at risk healthcare workers. The majority (3 out of 4 who responded to our enquiry) reported a sensitivity of 80%. Assuming a prevalence of hand dermatitis among healthcare workers of 15%, and a high sensitivity of 0.90% with a width of confidence interval 0.10 (targeting a lower bound for sensitivity of 0.80), the estimated required sample size is 231. We hypothesised the same prevalence for clinical and non-clinical staff, and also for staff of light, medium and dark skin. This totals 1386 participants (i.e. 231 participants for each of the 6 groups clinical/non-clinical staff and type of skin), which would give sufficient power for any analysis stratification. We aim to recruit approximately equal numbers (~460 participants) from each of the 3 sites in the study.

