There is a statutory responsibility under the COSHH Regulations 2002 for employers to carry out health surveillance for hand dermatitis in workers exposed to a known hazard in the workplace and where there is potential for significant exposure.(9) As many healthcare workers are unavoidably exposed to frequent wet work in their roles due to frequent or prolonged contact with water, the Health and Safety Executive considers that they should be under regular high-level health surveillance.(10) The reality of introducing such a programme in the healthcare setting is a challenge, not least because it raises practical and logistical issues which need to be carefully considered; for example which questionnaire should be used for health surveillance or, who should do the visual inspection of a worker's skin if dermatitis is suspected? The Nordic Occupational Skin Questionnaire (NOSQ)(11) is a validated tool but even its short form is four pages long, rendering it impractical for use in a large health surveillance programme in the National Health Service. Consequently, the statutory requirement is frequently not enforced in the health service and hand dermatitis is often not picked up until relatively late in the disease, making it harder to treat and increasing the risk of them being unable to continue to work.

The single-item questionnaire has been used before. As a component of a large randomised trial (SCIN trial: Skin care intervention in nurses) of an intervention to prevent hand dermatitis in intensive care and student nurses, we tested the accuracy of NHS nurses' self-assessment of hand dermatitis, using a simple question screening tool ('In your opinion do you have hand/wrist dermatitis?' with answer options of yes/no or unsure); if they reported having dermatitis they were asked to state where on the hand / wrist the dermatitis was. We compared their self-assessment with assessment by dermatologists using hand photographs. (5) The method was feasible and acceptable, as was that employed by the Danish study of hairdressers' dermatitis who self-assessed hand dermatitis when using a screening questionnaire adapted from NOSQ. (12)

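### Section 12.1 promises sufficient power for any stratification, but 231 per group comes from a precision formula that meets its target only at an unsourced sensitivity of 0.90

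*Protocol*

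**What the plan says.** Section 12.1 takes sensitivity as the primary outcome ("Considering as the primary study outcome the sensitivity of the single-item questionnaire"). The inputs to the sample size are:

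- **Prevalence:** "Assuming a prevalence of hand dermatitis among healthcare workers of 15" per cent.
- **Sensitivity and precision:** "a high sensitivity of 0.90% with a width of confidence interval 0.10", with the stated aim of "targeting a lower bound for sensitivity of 0.80". The 0.80 comes from a small survey of occupational physicians ("The majority (3 out of 4 who responded to our enquiry) reported a sensitivity of 80" per cent). No source is given for the 0.90.
- **Result:** 231 per group, multiplied by six groups (clinical or non-clinical staff, by light, medium or dark skin) to give 1386. This is described as a number "which would give sufficient power for any analysis stratification".

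Section 12 reports sensitivity "along with its 95% confidence intervals when compared with the gold standard". It does so first in all participants and then by two hand-washing risk levels (RQ1). For RQ2 it estimates accuracy in clinical and non-clinical staff, tests the difference between them, and stratifies by Fitzpatrick phototype.

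The Introduction (section 2) reports that the team had already tested a very similar single question in nurses: "We compared their self-assessment with assessment by dermatologists using hand photographs". It does not give the sensitivity found.

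**The concern.** The closing assurance in section 12.1 covers every stratified analysis, but the calculation behind it supports less, for two reasons.

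First, the formula fixes the width of a confidence interval. It says nothing about the power to detect a difference between groups, and section 12 plans such a test.

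Second, the width depends on the sensitivity assumed. Above one half, a proportion is estimated more precisely the closer it is to 1, so 0.90 gives a tighter interval than 0.85 or 0.80 would. The value is applied to every group without a source, while RQ2 exists partly to find phototypes where the questionnaire is less accurate.

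At stake is how the RQ2 results are read. If sensitivity in a group is around 0.80 to 0.85, its interval will be wider than planned. A non-significant clinical versus non-clinical difference could also be taken as evidence of similar accuracy, because the protocol says the power was sufficient.

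**Working it through.** **Inputs from the protocol.** Sensitivity Se = 0.90, d = 0.10, prevalence 0.15, and 231 per group in six groups (all section 12.1). The confidence level is 95% (section 12), taken as two-sided with z = 1.96. The range 0.70 to 0.90 for the true sensitivity is my assumption. The margins assume the planned equal groups.

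**Step 1: reproduce 231.**
n = z² × Se × (1 − Se) / d² / prevalence = 3.8416 × 0.90 × 0.10 / 0.01 / 0.15 = 34.57 / 0.15 = 230.5, rounded up to 231.
So 0.90 is the value used, and 0.10 is a half-width (0.90 − 0.10 = 0.80). Read literally as a full width (d = 0.05), it would give 922, not 231.

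**Step 2: expected cases at 15% prevalence.**
- Group: 231 × 0.15 = 34.65
- Skin-type margin: 462 × 0.15 = 69.3
- Clinical or non-clinical margin: 693 × 0.15 = 103.95
- Whole sample: 1386 × 0.15 = 207.9

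**Step 3: precision at each level.** Half-width = 1.96 × √(Se(1 − Se)/cases). Entries are half-width / lower limit.

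| Se | Group of 231 | Skin type, 462 | Clinical or not, 693 | All, 1386 |
|---|---|---|---|---|
| 0.90 | 0.100 / 0.800 | 0.071 / 0.829 | 0.058 / 0.842 | 0.041 / 0.859 |
| 0.85 | 0.119 / 0.731 | 0.084 / 0.766 | 0.069 / 0.781 | 0.049 / 0.801 |
| 0.80 | 0.133 / 0.667 | 0.094 / 0.706 | 0.077 / 0.723 | 0.054 / 0.746 |
| 0.75 | 0.144 / 0.606 | 0.102 / 0.648 | 0.083 / 0.667 | 0.059 / 0.691 |
| 0.70 | 0.153 / 0.547 | 0.108 / 0.592 | 0.088 / 0.612 | 0.062 / 0.638 |

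The lower limit reaches 0.80 from a sensitivity of about 0.90 (group of 231), 0.88 (skin type), 0.87 (clinical or non-clinical) and 0.85 (whole sample). Holding the half-width at 0.10 in a group would take 327 participants at 0.85, 410 at 0.80 and 538 at 0.70.

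**Step 4: chance of reaching the 0.80 limit in a group when the true sensitivity is 0.90.** With 35 cases, the Wald lower limit is at least 0.80 when 32 or more are detected: P(X ≥ 32 | 35, 0.90) = 0.53. Wilson and exact limits need 33 or more: P = 0.31. At a true 0.85 the chances are 0.21 and 0.09.

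**Step 5: power of the clinical versus non-clinical comparison.** Take about 104 cases per arm and assumed sensitivities of 0.90 and 0.80.
SE = √(0.90 × 0.10/104 + 0.80 × 0.20/104) = √(0.25/104) = 0.049.
z = 0.10/0.049 = 2.04.
Power ≈ Φ(2.04 − 1.96) = Φ(0.08) ≈ 0.53.

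**The case against.** The strongest reply is that the primary analysis is not at risk. RQ1 is answered in all participants, where the half-width is at most 0.068 whatever the sensitivity (its value at 0.50). The six cross-classified groups are a sizing device, since section 12 does not list clinical status by skin type as an analysis. The margins it does use keep a half-width below 0.10 down to sensitivity 0.80 (0.077 and 0.094) if the groups are equal, and subgroup accuracy is described as explored. All of this stands and limits the point. It does not rescue the blanket assurance. Section 12 stratifies by the six individual phototypes, which would hold about 231 each even if evenly filled. It also plans a statistical comparison that the calculation never addressed.

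Some stronger readings are tempting, but the documents do not support them:

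- **That the design fails wherever the tool is less than excellent.** This is true of groups of 231, not of the whole sample.
- **That 0.90 is a best case.** The protocol openly calls it high, and 0.95 would need only 122 per group. Any plan aiming at a lower limit of 0.80 has to assume more than 0.80.
- **That 0.90 contradicts the team's own data.** The earlier sensitivity is not in the protocol. The earlier sample was intensive care and student nurses, whereas ICU nurses and students on placement are now excluded, so the result may not transfer.
- **That the printed 0.90% spoils the sample size.** The same sentence targets 0.80, and only 0.90 fits both that target and 231.

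**Conclusion.** The point holds as a fault in what section 12.1 claims, not in the number recruited. The figure of 231 is arithmetically correct for its stated inputs, but it delivers a 0.10 half-width in a group only if sensitivity is at least 0.90. At 0.80 the half-width is a third larger (0.133). Even at exactly 0.90, meeting the 0.80 lower limit in a group is roughly an even chance with Wald limits and less with Wilson. Power for a 0.10 difference between clinical and non-clinical staff is about 53%, so the claim of sufficient power for any stratification is not supported.

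The whole-sample estimate of sensitivity is adequately precise. These figures rest on 15% prevalence in every group, equal group sizes, and assumed sensitivities of 0.70 to 0.90. Section 7.1 plans convenience sampling, so equal groups are an aim rather than a guarantee.

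**What to change.** Revise section 12.1, keeping N at 1386:

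1. Print the planning sensitivity as 0.90 (90%) and call 0.10 a half-width.
2. Give the rationale for 0.90, including whether the team's earlier study in nurses supports it or why it does not apply.
3. Withdraw the statement about sufficient power for any stratification.
4. Replace it with a short table of expected half-width and lower limit over an assumed sensitivity of 0.70 to 0.90, for the whole sample, the clinical/non-clinical and skin-type margins, and groups of 231.
5. State that a lower limit of 0.80 is expected only from a sensitivity of about 0.85 in the whole sample or 0.90 in a group of 231.
6. State that group-level results and differences between groups are exploratory.

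The cost is a few lines of text, with no extra participants and no change to the primary analysis. The downside is that the stated precision looks less favourable than it does now.

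### Section 12.1 gives a confidence interval width of 0.10 for 231 per group, but 231 delivers a width of about 0.20, and the 0.80 lower bound is met at that size only by a Wald interval that undercovers

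*Protocol*

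**What the plan says.** Protocol section 12.1 builds the sample size on the sensitivity of the single-item question. The inputs are:

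- Prevalence: "Assuming a prevalence of hand dermatitis among healthcare workers of 15"%.
- Sensitivity and precision: "a high sensitivity of 0.90% with a width of confidence interval 0.10". The percent sign after 0.90 is a typing slip.
- Target: "targeting a lower bound for sensitivity of 0.80". This matches the minimum acceptable value obtained from occupational physicians: "The majority (3 out of 4 who responded to our enquiry) reported a sensitivity of 80"%.

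The result is stated as "with a width of confidence interval 0.10 (targeting a lower bound for sensitivity of 0.80), the estimated required sample size is 231", multiplied up as "231 participants for each of the 6 groups clinical/non-clinical staff and type of skin" to give 1386. The section then says that this is enough power whatever stratification is analysed.

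Section 12 (Statistical considerations) promises sensitivity "along with its 95% confidence intervals when compared with the gold standard", first in all participants and then by hand-washing risk. Under RQ2 it compares clinical with non-clinical staff and stratifies by the six Fitzpatrick phototypes. Neither section names an interval method.

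**The concern.** The sentence does not agree with itself. An interval of full width 0.10 centred on 0.90 ends near 0.85, not 0.80. The stated width, the stated lower bound and the stated N therefore cannot all be true.

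The lower bound is also fragile. About 35 cases per group means only three or four expected false negatives, and the normal approximation is poor there.

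The 0.80 bound is the protocol's only precision target and is tied to the minimum acceptable sensitivity. If a group of 231 cannot be expected to deliver it, a questionnaire that truly reaches 0.90 may look inadequate in a particular staff-by-skin group or phototype when the group is merely small. That bears on RQ2, which the synopsis lists among the primary objectives.

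**Working it through.** **Inputs.** Sensitivity 0.90, prevalence 0.15, lower bound 0.80, 231 per group, six groups (all section 12.1); 95% confidence (section 12), taken as two-sided, z = 1.96.

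**1. Reproducing 231.** The Wald formula is N = z² × Se × (1 − Se) / (d² × prevalence), with d the half-width.

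- d = 0.10: 1.96² × 0.9 × 0.1 / 0.01 = 34.57 cases; 34.57 / 0.15 = 230.5, so 231. This reproduces, and 6 × 231 = 1386.
- d = 0.05 (a full width of 0.10): 138.3 cases; 138.3 / 0.15 = 922. This does not reproduce.
- One-sided 95% versions give 163 and 650, which do not reproduce either.

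So 0.10 was used as a half-width, and the full width is 0.20.

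**2. The interval at 231.** Expected cases are 231 × 0.15 = 34.65. With an estimate of 0.90:

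| Method | 95% interval | Width |
|---|---|---|
| Wald | 0.800 to 1.000 | 0.20 |
| Jeffreys | 0.769 to 0.968 | 0.20 |
| Wilson | 0.757 to 0.963 | 0.21 |
| Exact (Clopper-Pearson) | 0.750 to 0.976 | 0.23 |

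The width is about 0.20 or more under every method. Only Wald has its lower limit at 0.80.

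With whole counts in 35 cases, 31/35 has a lower limit of 0.740 (Wilson) or 0.733 (exact). For 32/35 the limits are 0.776 and 0.769. The Wald limits are 0.780 and 0.822.

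**3. Wald coverage.** Summing the Binomial(35, 0.90) probabilities of all outcomes whose Wald interval contains 0.90 gives 0.871, against a nominal 0.95.

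**4. Chance of reaching the target in one group of 231.** Take cases ~ Binomial(231, 0.15), with a 5th to 95th percentile range of 26 to 44, and detected ~ Binomial(cases, 0.90). Then P(lower limit ≥ 0.80) is 0.53 (Wald), 0.27 (Wilson) and 0.25 (exact).

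**5. Larger sets, same assumptions, estimate 0.90.**

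| Set | N | Expected cases | Wilson lower limit | P(Wilson lower limit ≥ 0.80) |
|---|---|---|---|---|
| One of three skin groups | 462 | 69 | 0.807 | 0.58 |
| One of two staff groups | 693 | 104 | 0.827 | 0.78 |
| Whole sample | 1386 | 208 | 0.852 | 0.98 |

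For the lower limit to be 0.80 at an estimate of 0.90, Wilson needs 62 cases (62 / 0.15 = 413.3, so 414 participants). The exact interval needs 65 cases (434 participants).

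**6. Margin in the skin groups.** From 462 to 414 is a loss of 48, or 48 / 462 = 10%. From 462 to 434 is a loss of 28, or 6%. Poor photographs are excluded from the analysis (section 7.3) and sampling is by convenience (section 7.1), so neither equal groups nor full numbers are assured.

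**7. Fitzpatrick phototypes.** Six phototypes split equally would again give 1386 / 6 = 231 each. Any imbalance leaves some of them smaller.

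**The case against.** The best defence is that 231 is correctly calculated. The same sentence gives 0.90 and a lower bound of 0.80, so a margin of 0.10 was plainly meant and the word width is a slip. The protocol names no interval method, that choice is often left to the SAP, and under the formula used the expected lower limit is indeed 0.80. The protocol also claims no assurance probability, and section 12 describes the subgroup work as exploratory.

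Much of this stands. It does not rescue the text, for two reasons. The stated width is wrong under every method. And the 0.80 limit at 231 is a numerical property asserted in the protocol itself, which holds only under an interval that falls well short of its nominal 95%. A later choice of method in the SAP can confirm Wald and its undercoverage, or abandon the 0.80 limit at 231; it cannot keep both the limit and the coverage.

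A reader might infer three stronger things that the documents do not support:

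- **That 231 is a miscalculation and 922 per group are needed.** The stated lower bound of 0.80 rules out a full width of 0.10 as the aim.
- **That the study is too small for its primary outcome.** The primary outcome is sensitivity in all participants, where about 208 cases give ample precision.
- **That the design fails because all six groups are unlikely to clear 0.80 together.** The plan sets no such joint criterion and does not list the staff-by-skin cells as an analysis.

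**Conclusion.** The point holds as a false statement of precision, not as an error in the calculation of 231. The full width at 231 per group is about 0.20, twice what is stated. The 0.80 lower bound at that size exists only under a Wald interval with about 87% actual coverage. With Wilson or exact intervals the limit is about 0.76 or 0.75, and it reaches 0.80 in roughly one group in four. The general claim about stratified analyses is therefore unsupported for the six staff-by-skin groups and for the six individual phototypes.

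These results use the protocol's own 0.90 and 15%; they do not depend on either being optimistic. The size of the lower-bound shortfall depends on the method (0.750 to 0.769 across exact, Wilson and Jeffreys). The whole-sample analysis is sound. The two staff groups are adequate in expectation and the three skin groups marginally so, but only if groups are equal in size and few photographs are lost.

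**What to change.** Keep 1386 and reword section 12.1:

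- Replace the width of 0.10 with a half-width of 0.10 (Wald), or with the interval achieved. Correct 0.90% to 0.90.
- State that 231 per group gives about 35 cases and, at an observed sensitivity of 0.90, a 95% Wilson interval of about 0.76 to 0.96.
- Delete the claim of enough power for any stratification, or limit it as follows. The 0.80 lower bound is expected for the whole sample (about 0.85). If groups are equal in size and few photographs are excluded, it is also expected for the two staff groups (693 each, about 0.83) and marginally for the three skin groups (462 each, about 0.81; about 414 assessable participants are needed). It is not expected for the six staff-by-skin groups or the six individual Fitzpatrick phototypes.
- Use Wilson or exact intervals for sensitivity, in section 12 or in the SAP.

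The cost is a few sentences and a less favourable stated precision for the small strata. No participants are added, and neither the outcome nor recruitment changes.
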